**NCT04086693**

**6/16/2020**

# **Peripheral Intravenous Catheter Securement with Tissue Adhesive Compared to Conventional Dressing: A Randomized Controlled Trial**

## **Background/Scientific Rationale:**

Nearly all hospitalized patients require intravenous (IV) access for treatment. Patients rely on functional vascular access to receive life saving IV therapies. Generally, peripheral IVs have high failure rates with 19-25% of IVs failing prior to completion of therapy and 45-56% of ultrasound-guided peripheral IVs failing prior to completion of therapy. Dislodgment, infiltration/extravasation, and phlebitis are common complications that lead to early failure. IV restarts are a common procedure and are unfortunately simply a part of a normal workday for nurses. A failure rate of up to 56% in a technology that is over 75 years old is unacceptable.

If access is lost, patients may experience treatment delays, dissatisfaction from repeat needle-sticks, and health complications if the patient's condition becomes critical. IV failure can result in a number of negative health/quality outcomes including phlebitis and infections and/or skin necrosis from caustic medication infiltration; utilization of invasive procedures such as peripherally inserted central catheters (PICC) and central lines; and wasted medical/nursing time.

Because failure rate is high, it is important to approach insertions methodically to improve survival rates. One area of opportunity is securement of the catheter. Accidental dislodgment is a common cause of early IV failure accounting for up to 50% of catheter failures. Beyond dislodgment, inadequate fixation of the catheter to the patient's skin causes micromotion, leading to vein irritation and entry of skin bacteria into the entry site. This micromotion leads to phlebitis, occlusion, and infection. Standard practice for securement involves placement of a polyurethane dressing with clear tape. A variety of additional devices are available on the market including tissue adhesives, specially designed securement dressings, and sutureless securement devices. The evidence suggests the use of tissue adhesives may decrease peripheral IV failure with a decrease in dislodgments and occlusions compared to the alternatives. Bugden et al. found that skin glue reduced catheter dislodgment by 7% and reduced peripheral IV failure by 10%.

While some evidence supports the use of tissue adhesives for securement, further randomized controlled trials are needed to assess the effectiveness of this intervention. Further, only one prospective, randomized trial evaluated patients in the emergency room setting. Nearly 50% of all hospital admissions start in the emergency department (ED) and 80% of hospitalized patients require IV access. This highlights the importance of understanding the impact of tissue adhesives on peripheral IV survival for patients admitted through the ED. While Bugden found that skin glue reduced IV failures for patients hospitalized from the

ED, patients were only followed for 48 hours. The general consensus is to continue using IVs as long as there is no clinical indication for removal. As the average hospital length of stay in the United States is 4-6 days, it is clear that the 48 hour cutoff is a critical flaw in the analysis and further investigation over a longer time period is urgently needed.

We propose a prospective randomized controlled trial to evaluate peripheral IV failure with ED patients that are hospitalized comparing securement with standard securement plus Adhezion Biomedical SecurePortIV™ to standard securement.

**Specific Aim 1:** Test the prediction that the experimental securement solution of standard dressing plus Adhezion Biomedical SecurePortIV™ will have a lower probability of failure compared to the control standard of care securement.

For Aim 1, an improved survival of the experimental securement solution will be evaluated by functionality of catheter for intravenous therapy prior to patient discharge. The event is failure of functionality identified during follow-up assessment during hospitalization. Duration of dwell and functional failure of the catheter will be employed to estimate catheter survival.

**Specific Aim 2:** Determine the difference in cause-specific IV failure rates between the experimental and control groups. Specific etiologies to be evaluated include dislodgment, infection, phlebitis, and occlusion.

**Specific Aim 3:** Determine the difference in costs associated with the experimental group versus the control group. Cost calculation will include all costs of placement in each group: labor and material.

## **Study Design:**

We propose a prospective, single-site, parallel, two-arm randomized investigation of catheter survival when securement strategies are evaluated. Specifically, conventional securement with polyurethane dressing and tape will be compared with experimental securement with tissue adhesive, polyurethane dressing and tape. The primary objective of this study is to demonstrate that there is better survival of the catheter securement with the tissue adhesive. Exploratory secondary and adjusted multivariable analyses will also be conducted.

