A tourniquet may be applied as needed. If the patient is actively receiving an infusion, the drip will briefly be halted to evaluate for functionality. Functionality will be assessed with the existing dressing in place. If the catheter is functional and free of any signs of complications, study subjects will be randomized by a computer generated 1:1 envelope system to either the control group: polyurethane dressing + clear tape or the experimental group: polyurethane dressing + clear tape + tissue adhesive. If the IV is not functional, a new catheter will be inserted in a new location, documented, and patient continues in the study. For the control group, the polyurethane dressing will be gently removed. Dressing will be removed carefully to minimize any potential dislodgments or skin injury. The site will be evaluated for oozing or blood and as needed cleaned with sterile gauze. Once the site is completely dry, a new polyurethane dressing will be applied and reinforced with tape in a standard fashion. See Appendix A for pictures depicting standard dressing application with tape. Once securement is complete, functionality will be reassessed per protocol above. For the experimental group, the existing securement will be gently removed. The site will be evaluated for oozing or blood and as needed cleaned with sterile gauze. Once the site is completely dry, the tissue adhesive will be applied per directions in Appendix B. A new standard polyurethane dressing will be applied and tape will be applied per the standard approach. Once securement is complete, functionality will be reassessed per protocol above. The time of the new dressing application will be noted as time zero. Catheter dwell time will begin at this point.

Additional data variables collected at the initial assessment include: demographics such as age, sex, INR > 1.5, platelets < 50, insertion site details, hours from insertion to recruitment, inserter credentials.

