Appendix E represents the data collection documentation tool for all catheter follow-ups.

## **Statistical Rationale and Analysis Plan:**

### ***Sample Size and Power Analysis***

For this randomly allocated two-groups experiment, the primary outcome is catheter survival associated with securement devices. Sample size calculation is based on primary outcome: composite or all cause premature removal due to complication of the IV catheter. Based on existing literature, the maximum mean failure rate across major investigations is 25% which functions as the estimated failure rate of the standard of care group. Assuming a minimum difference of 10% needed for prompting a change in practice and based on existing literature, the experimental group (standard of care plus tissue adhesive) is hypothesized to have a composite failure rate of 15%. 154 subjects per group for a total sample size of 308 subjects is the minimum recommendation assuming a 10% dropout rate. To account for a larger dropout percentage, 350 patients or 175 subjects per group is the final sample size to provide 80% power to detect a significant effect.

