### ***Statistical Analysis***

Characteristics of enrolled patients will be summarized using means [standard deviations] and medians [interquartile ranges] for continuous variables, and frequencies (percentages) for categorical variables. Exploratory data analyses including histograms, Pareto charts, scatter plots, and box plots will be further used to show the distribution. Appropriate transformations and estimation procedures will be performed as necessary. To test the effect of securement strategies on each of aims, we will further use Cox proportional hazard regression models for time-to-event outcomes and logistic regression models for binary outcomes. P-values of less than 0.05 will be considered statistically significant. Analysis will be conducted using SAS 9.4.

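### The primary Aim 1 Cox test appears to use arm alone; prespecifying a short baseline adjustment would cost only wording and may recover some power

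*Combined protocol and SAP*

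**What the plan says.** The Study Design section gives the primary objective as better catheter survival with the adhesive. It then adds: "Exploratory secondary and adjusted multivariable analyses will also be conducted". The Statistical Analysis section says that "we will further use Cox proportional hazard regression models for time-to-event outcomes and logistic regression models for binary outcomes". It lists no covariates and does not say whether the primary model is adjusted. The significance rule is "P-values of less than 0.05 will be considered statistically significant", with no statement of one or two sides.

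The Initial Assessment section lists what is recorded at enrolment: "demographics such as age, sex, INR > 1.5, platelets < 50, insertion site details, hours from insertion to recruitment, inserter credentials". Allocation is 1:1 by envelope, and no stratification is described, so neither the randomization nor the named primary model uses these variables.

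On power, the Sample Size and Power Analysis section takes 25% failure in the control group and 15% in the experimental group. It states that "154 subjects per group for a total sample size of 308 subjects is the minimum recommendation assuming a 10% dropout rate", and then that "350 patients or 175 subjects per group is the final sample size to provide 80% power to detect a significant effect".

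**The concern.** If adjusted models are exploratory, the comparison that decides Aim 1 ignores baseline information the trial already pays to collect. In a Cox model, leaving out a covariate that truly predicts failure moves the estimated hazard ratio towards 1 and lowers the power of the arm test. Randomization protects the validity of the unadjusted test, but does not give that power back.

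This would matter little in a trial with power to spare. Here the stated 80% cannot be reproduced, so a gain that needs no extra patients deserves a look.

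If the plan instead means to leave the primary model open, a different problem arises. The covariate set could then be chosen after outcomes are known, with an adjusted and an unadjusted result both to hand. The same edit settles both cases.

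**Working it through.** **Inputs from the documents.** Failure 25% versus 15%; 175 per arm; 80% power; alpha 0.05 (Sample Size and Power Analysis; Statistical Analysis). Exclusion of 10-15% (Exclusion Criteria). **Assumptions.** Two-sided test; the 25% and 15% rates apply to the patients analysed; covariate strength as set out in step 4.

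**1. The plan's own sample size.** For two proportions, n per arm = [1.960 × √(2 × 0.20 × 0.80) + 0.842 × √(0.25 × 0.75 + 0.15 × 0.85)]² / 0.10² = (1.1087 + 0.4724)² / 0.01 = 250. Allowing for 10% dropout, 250 / 0.9 = 278. A one-sided test needs 197, or 219 after dropout. Neither gives 154 or 175.

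On the survival scale, the hazard ratio is ln 0.85 / ln 0.75 = 0.565. Schoenfeld's formula gives 4 × (1.960 + 0.842)² / (ln 0.565)² = 97 events. At a 20% average failure rate that is 97 / 0.20 = 485 evaluable patients.

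**2. Power at the planned size.** For proportions, power = Φ{(0.10 × √n − 1.1087) / 0.5612}. For Schoenfeld, power = Φ{0.571 × √events / 2 − 1.960}, with events = 0.20 × 2n.

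| Per arm | Events | Proportions | Schoenfeld |
|---|---|---|---|
| 175 (no loss) | 70 | 64.9% | 66.6% |
| 157 (10% loss) | 62.8 | 60.1% | 61.9% |
| 149 (15% loss) | 59.6 | 57.9% | 59.7% |

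One-sided power at 175 per arm is still only 75.8% (proportions) or 77.2% (Schoenfeld).

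**3. Why adjustment can help.** Hold observed failure at 25% and 15%, and let baseline covariates account for a given SD of the log hazard. The hazard ratio within covariate levels is then further from 1 than 0.565. It is 0.555 at SD 0.5 and 0.522 at SD 1.0.

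**4. Size of the gain.** Simulated trials, 4,000 per setting, with four baseline covariates, administrative censoring only, and a two-sided Wald test of arm. Monte Carlo error is about 0.8 points per power figure.

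| Assumed SD | 175 per arm: arm only → adjusted | 157 per arm: arm only → adjusted |
|---|---|---|
| 0 | 64.0% → 64.0% | 60.3% → 60.1% |
| 0.3 | 65.9% → 66.5% | 61.0% → 62.0% |
| 0.5 | 64.4% → 67.3% | 59.7% → 62.2% |
| 0.8 | 63.4% → 70.3% | 58.6% → 65.3% |
| 1.0 | 65.0% → 75.6% | 59.6% → 70.2% |

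**5. More model terms.** Age, four sites, hours and credentials need six or more terms. With six terms at 175 per arm, power goes from 64.0% to 63.7% if the covariates are useless. The gain is about 0-2 points at SD 0.3-0.5, about 5 at SD 0.8 and about 11 at SD 1.0. With seven terms (1,500 trials per setting, error about 1.2 points) the figures are 65.6% to 64.8% at SD 0, 66.2% to 67.9% at SD 0.5, and 66.1% to 75.7% at SD 1.0.

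**6. What the SDs mean.** SD 0.5 implies exp(2 × 0.5) = 2.7 times the hazard for a patient one SD above the mean compared with one SD below. SD 1.0 implies exp(2.56) = 13 times between the 10th and 90th percentiles.

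**The case against.** **The plan never says unadjusted.** A reader might infer that the plan commits to an arm-only primary model. It does not. Study Design lists adjusted analyses as additional, and its grammar leaves some doubt about whether the word exploratory governs them; Statistical Analysis is silent. This stands, and the arm-only reading is an inference. The need to fix the primary model in advance does not depend on it.

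**An arm-only test is valid.** A reader might take this point for an error in the plan. It is not one: allocation is 1:1 with no stratification described, so nothing obliges adjustment. This is a matter of efficiency.

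**Prognostic strength is unknown.** No section calls any collected variable a predictor of failure or gives its effect. Eligibility also narrows their spread: enrolment within 8 hours of insertion, four sites, 18 or 20 gauge, no ultrasound-guided insertion. A 13-fold contrast is hard to credit under those limits. This stands, and it makes the upper end of the range the less likely one.

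**Too many terms for the events.** After 10-15% exclusion about 60-63 events remain, and the restriction to dwell over 48 hours may remove more. Seven parameters would have about 60 / 7 = 8.6 events each. The simulations with six and seven terms show no material loss at 175 per arm, but sparse categories should be grouped.

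**The shortfall is a sample-size problem.** A reader might infer that adjustment rescues the stated 80%. It does not: even at SD 1.0 with no exclusions, adjusted power is about 76%.

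**Conclusion.** The point holds as an efficiency and prespecification improvement. On the natural reading, the primary Aim 1 Cox test uses arm alone; that is valid but may waste baseline information already collected. At the plan's own rates, two-sided power is about 65-67% with all 350 patients and about 58-62% after 10-15% exclusion. Adjustment would add about 0-3 points for covariates with a log-hazard SD up to 0.5 and about 5-11 points for SD 0.8-1.0, with practically no loss if they carry no information.

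The SDs are assumptions, so the lack of prespecified covariates and the direction of the effect are firmer than the size. The figures also take 25% and 15% as the rates among analysed patients, although failures before 48 hours are not counted.

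**What to change.** In Study Design and Statistical Analysis, define the primary Aim 1 test as the arm coefficient from a Cox model that also contains age, insertion site, hours from insertion to recruitment (the variable actually collected) and inserter credentials. Fix this list before outcome data are seen.

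- Group sparse site and credential categories in advance, to suit about 60-70 events.
- A non-functioning catheter may be replaced at enrolment, so take site and hours from the catheter in place and secured at time zero. State how hours are coded for a replacement.
- Exclude variables that arise after randomization, such as medications given through the catheter (Follow-up Assessment).
- State that the hazard ratio is conditional on the covariates.
- Report the arm-only Cox model as supportive.

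Correct the 80% power statement separately; this change does not do that. The cost is wording only, with no new data and no extra patients. The one trade-off is that the headline hazard ratio becomes conditional rather than marginal.

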## ***Pre-Enrollment Staff Training:***

The proper application of the tissue adhesive requires some education and training of staff. Research staff performing patient enrollments will be trained to place the tissue adhesive by the Adhezion clinical/education team. A possible training may include a short didactic and hands-on session and application of the solution on

healthy volunteers/patients. Enrollment will begin once staff are deemed proficient in the procedure.

***Study Population and Eligibility:***

**Inclusion Criteria:**

A convenience sample of patients with expected greater than 48 hours admission likelihood will be eligible for enrollment.

1. All adult patients greater or equal to 18 years of age
2. Admission from the ED to a progressive floor expected for over 48 hours OR 2a: Admission from ED to any floor type with express approval from the Principal Investigator
3. IV placement in the antecubital fossa, forearm, wrist or hand
4. IV placement in the Emergency Department
5. Enrollment within 8 hours of IV insertion
6. 18 or 20 gauge 1.16 inch IV catheter

**Exclusion Criteria:**

1. Patients with ultrasound-guided IV insertions
2. Alternate site of cannulation
3. Voluntary withdrawal
4. Patients with a non-standard polyurethane dressing
5. Known allergy to cyanoacrylate or formaldehyde

The survival analysis will only be performed on patients that have an IV dwell time greater than 48 hours. Over 85% of patients admitted to a progressive floor have length of stay greater than 48 hours. The sample size calculation reflects an assumed 10 - 15% exclusion rate.

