**Study Procedure:**

***Initial Assessment:***

Patients admitted from the ED to a progressive floor are eligible participants. Research staff will approach a convenience sample of patients admitted to the progressive floors based on screening of the electronic medical record. These patients are admitted to a progressive floor but approached by research staff when physically in the emergency department waiting for a room assignment. The principal investigator may also choose to include additional patients admitted to non-progressive inpatient units. The principal investigator will inform the research staff when such cases arise. Similar to other study subjects, these patients will be approached in the Emergency Department. If the patient agrees to participate in the

trial, the study subject will be consented by the research staff. Research staff will confirm functionality of the existing IV previously placed by ED staff. The assessment will include observing for blood return into the tubing upon aspiration and/or unobstructed flush with a minimum of 1-2 ml of normal saline. Staff will also observe the site for any signs of redness or tenderness.

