### ***Follow-up Assessment:***

After initial assessment, the catheter will be assessed by the research team every 24 +/- 5 hours as long as the patient is hospitalized up to 7 days or 168 hours. At each follow up interval the researcher notes the date/time of evaluation and assesses for any signs and symptoms of complications and functionality of the device. A catheter is functional if the IV flushes without resistance. Catheters will be assessed daily for signs and symptoms of complications. See Appendix C for details regarding the assessment for complications. Any signs or symptoms of complications or lack of functionality will be reported to the patient's primary care team so that management of the IV catheter can be addressed. If the catheter and adhesive are removed early due to catheter failure or complication, or for patient discharge prior to 7 days a medical adhesive remover may be used.

If the catheter was identified to have any signs or symptoms of complications during follow-up assessment the date and time of observation of the complication will be documented in the data collection tool and the primary team will be notified of the complication. If the catheter was removed prior to the follow-up assessment then the IV removal time and the reason for removal will be obtained through chart review. For all catheters removed due to a complication, re-insertion attempt data will be tracked through the medical record in the nursing section for venous lines and need for reinsertion of the IV or escalation to a midline, PICC, or CVC will be noted. If the patient is discharged prior to the time of follow-up assessment then the time of discharge will be documented and the IV will be presumed functional until time of discharge unless otherwise noted in the chart.

The medication administration record will be queried for all medications given through each catheter with specific attention to antibiotics and anticoagulants. Vesicants/irritants that are generally given via central line or considered caustic to the vessel will be noted in both groups. Number of doses will be recorded. See Appendix D for full list of non-neoplastic vesicants.

Additional data gathered by research staff on follow-up evaluation includes: dwell time in days/hours, hospital length of stay, and number of peripheral IVs for duration of stay.

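### Voluntary withdrawal is listed as an exclusion criterion, and no rule keeps a randomised patient who withdraws in the analysis

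*Combined protocol and SAP*

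**What the plan says.** Item 3 of the Exclusion Criteria is "Voluntary withdrawal". The other four items (ultrasound guidance, cannulation site, dressing type, allergy) can be settled at enrolment.

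Initial Assessment gives the order of events. A patient who agrees to take part is approached first, and "the study subject will be consented by the research staff". The catheter is then checked, and patients are "randomized by a computer generated 1:1 envelope system".

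Directly below the exclusion list comes an analysis restriction: "The survival analysis will only be performed on patients that have an IV dwell time greater than 48 hours". The same paragraph adds: "The sample size calculation reflects an assumed 10 - 15% exclusion rate".

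Under Specific Aim 1, "The event is failure of functionality identified during follow-up assessment during hospitalization". Follow-up Assessment has the catheter checked about once a day "as long as the patient is hospitalized up to 7 days or 168 hours". For a patient discharged before the next check, "the IV will be presumed functional until time of discharge unless otherwise noted in the chart". There is no matching sentence for a patient who withdraws.

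Statistical Analysis names Cox and logistic models. It defines no analysis set, contains no intention-to-treat statement and gives no censoring rule.

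**The concern.** An exclusion criterion should be decidable before allocation. Refusal is already dealt with at consent, so withdrawal means leaving after having joined, and most of the time available for that lies after randomisation. As an exclusion, the item makes membership of the analysis depend on a later event.

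That event need not be independent of arm or outcome. The adhesive is the only planned difference between the arms, and the plan describes no masking of the patient. A patient may leave because of the dressing, or after a catheter has failed. These are possibilities; the documents report no reasons for withdrawal. If withdrawal is related to both arm and failure, removing those patients shifts one arm's failure rate and undermines the randomised comparison for Aim 1. If it is balanced, the main cost is some lost information, which the planned Cox model could have used.

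**Working it through.** **1. Does the item reach randomised patients?** The order is agreement, consent, function check, randomisation, follow-up. Withdrawal is possible in two windows: between consent and randomisation (a bedside check in the emergency department) and during follow-up (up to 168 hours). The second is far longer.

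**2. Does any rule keep them?** Follow-up Assessment covers discharge only, and Statistical Analysis covers no such case. Elsewhere the plan does take enrolled patients out for later events: the survival analysis requires dwell above 48 hours, and the Appendix E form directs staff to remove patients discharged within 48 hours of insertion. Literal exclusion of withdrawers would fit that practice.

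**3. Is there a figure in the plan to reproduce?** No withdrawal rate is given. The 10–15% exclusion allowance and the 10% dropout allowance are not broken down by cause. The sizes below therefore rest on assumed rates.

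**4. Illustration with no true effect.** From Sample Size and Power Analysis: n = 175 per arm and a 25% control failure rate, applied here to both arms. Assumed: a share w = 5% withdraws in the adhesive arm only, and a share f of those had a recorded failure first. The sum treats failure as a proportion and sets aside the 48-hour rule.

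- Adhesive patients left: 175 × 0.95 = 166.25
- Apparent adhesive rate: p_E = (0.25 − w·f)/(1 − w)
- d = 0.25 − p_E
- SE = √[0.25 × 0.75/175 + p_E(1 − p_E)/166.25]
- Chance of a false claim of benefit at two-sided 0.05, benefit direction only: Φ(d/SE − 1.96); nominal 2.5%

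| f | p_E | d | SE | False benefit |
|---|---|---|---|---|
| 50% | (0.25 − 0.025)/0.95 = 23.7% | +0.0132 | 0.0465 | Φ(−1.68) = 4.7% |
| 25% | (0.25 − 0.0125)/0.95 = 25.0% | 0 | 0.0469 | Φ(−1.96) = 2.5% |
| 10% | (0.25 − 0.005)/0.95 = 25.8% | −0.0079 | 0.0471 | Φ(−2.13) = 1.7% |
| 0% | 0.25/0.95 = 26.3% | −0.0132 | 0.0473 | Φ(−2.24) = 1.3% |

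The first row concerns few patients: 175 × 0.05 = 8.75 withdrawals, of which about 4.4 had failed. With 5% withdrawing in both arms and half of them failing first, both arms read 23.7% and the chance is again 2.5%.

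**5. Illustration with the planned effect (25% against 15%).** In the extreme case where every withdrawer had failed first:

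- 5% withdraw from adhesive, 2% from control: (0.25 − 0.02)/0.98 − (0.15 − 0.05)/0.95 = 23.5% − 10.5% = 12.9 points (from unrounded rates)
- 2% from adhesive, 5% from control: (0.25 − 0.05)/0.95 − (0.15 − 0.02)/0.98 = 21.1% − 13.3% = 7.8 points

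The planned difference is 10 points.

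**6. Balanced loss.** By the normal approximation, two-sided power for 25% against 15% is 64.9% with 175 per arm and 62.6% with 166.25 per arm (5% lost from each). That 64.9% is below the plan's stated 80% is a separate matter.

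**The case against.** The strongest reply is that two words in a list are weak evidence of an analysis rule. Where the authors want patients removed they say so, for short dwell and in Appendix E for early discharge; they write nothing similar for withdrawal. The item might cover only a patient who consents and changes their mind before the envelope is opened, which would be harmless. The 10–15% allowance also follows a sentence saying that over 85% of such patients stay beyond 48 hours, so it may reflect short stays alone.

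Part of this stands. A reader might infer that the plan orders recorded failures to be deleted. It does not say so, nor does it say they are kept; deletion is only the literal effect of excluding the patient. A reader might also infer that a catheter failing and removed on day 2 is lost because its patient later withdraws. That patient is already outside the survival analysis under the 48-hour rule, so only later failures are at issue here. Nor do the documents support a bias that must favour the adhesive: the direction depends on who leaves and when. Heavy withdrawal after failure is also doubtful, since what remains after catheter removal is largely chart review.

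What does not stand is that no change is needed. Even if the item covers only withdrawal before randomisation, the plan still does not say how a randomised patient who withdraws is analysed.

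**Conclusion.** Wrong as written. Followed literally, item 3 is a post-randomisation exclusion, and nothing in the plan overrides it. The size of any bias is unknown because no withdrawal rate is given. With 5% withdrawing in the adhesive arm only and no true effect, the chance of a false claim of benefit ranges from 1.3% to 4.7% as the share who had failed first goes from none to half, against a nominal 2.5%. It is exactly nominal when that share equals the 25% base rate. These figures assume one-sided loss, simple proportions and all failures analysable. If withdrawal is rare or balanced, the effect is small. The case for a change rests on an exclusion that is avoidable and has no benefit, not on a demonstrated large bias.

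**What to change.** Delete item 3 from the Exclusion Criteria. Add to Statistical Analysis that:

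- randomised patients who withdraw stay in their assigned arm;
- any failure up to withdrawal counts as an event;
- those without a failure are censored at the time of withdrawal;
- data already collected are used unless the patient asks for their removal, and the number of such requests is reported by arm.

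Reconcile this wording with the restriction of the survival analysis to dwell above 48 hours. That rule is a separate post-randomisation restriction, which this change does not resolve; without reconciliation the two sections could conflict.

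The cost is a few sentences. No new outcome data are needed beyond the date and time of withdrawal, and the planned Cox model handles the censoring.
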